The Dutch multicentre study into opportunistically screening Geriatric patients for Atrial Fibrillation using a PPG smartphone App; the Dutch-GERAf Study

Outline of the healthcare innovation project

Background of the project:

The latest European Cardiology Society's guideline (1. Kirchhof et al.) on the management of atrial fibrillation (AF) recommends opportunistic screening for people 65 years and older, and systematic screening might be considered in high risk population. The geriatric population that visits the outpatient service is such a population. Our previous work (2. Zwart et al., 3. Zwart et al.) showed that geriatric patients have a high rate of AF, and furthermore a very high rate of newly detected AF can be found when repeated screening is applied.

Since AF in elderly people often exists without symptoms, paroxysmal AF can easily remain undetected, and therefore untreated (2. Zwart et al.). Because geriatric patients have a very high risk of risk it is very relevant to identify cases of silent AF. To know the rate of paroxysmal AF helps to estimate the magnitude of the problem, and what the yield of repeated screening for AF might be in this population.

However, repeated screening for AF is not the common geriatric practise at this moment. It is very relevant to determine if comparable results are found when repeated screening is applied in multiple geriatric practises, and with a different method of detection. The primary goal of this innovation project is to assess the rate of newly detected AF when using a smartphone-based PPG detection app, and to determine if repeated screening for AF should become standard geriatric practise. This innovation project seeks to address those questions.

Photo-plethysmography (PPG) is a promising technology used in smartphones and smartwatches for heartrate and rhythm assessment. (6) To retrieve PPG measurements a photo-emitter of infrared light is coupled to a photo-receiver. The amount of infrared light absorbed or reflected by blood represents the systolic and diastolic phase. This technology has low costs and does not require additional hardware. Although easy to use and widely available, PPG measurements require good signal quality which may be affected by poorly perfused tissue or tremors. Especially in AF detection proper signal-noise assessment is important because of the irregular depolarization of the ventricles. To overcome these previous issues, we developed an automated PPG based diagnostic algorithm for the smartphone to detect AF. The test characteristics of this technique are robust and described elsewhere. (7)

Principal investigators and steering committee:

Dr. [name], cardiologist, Rijnstate hospital Arnhem

Dr. [name], geriatrician, North West Clinics, Alkmaar

Dr. [name], cardiologist Rijnstate hospital, Arnhem

Dr. [name], cardiologist, OLVG, Amsterdam

Dr [name], cardiologist, North West Clinics, Alkmaar

Participating centers:

Dijklander Hospital, Hoorn. Drs. [name], geriatrician.

Meander Medical Centre, Amersfoort. Drs. [name], geriatrician.

North West Clinics, Alkmaar. [name][name], geriatrician.

Rijnstate Hospital, Arnhem. [name], geriatrician.

Onze Lieve Vrouwe Gasthuis, Amsterdam. [name], cardiologist.

Aims of the project:

- a. To determine the rate of newly detected AF with repeated screening using a PPG based smartphone AF detection algorithm during follow-up visits at a geriatric outpatient center.
- b. To determine the rate of (paroxysmal) AF during follow-up visits.
- c. To evaluate the predictive value of a single measurement of NTproBNP at the baseline evaluation for the development of new AF.
- d. To evaluate the predictive value of the ABC Bleeding Risk Score, compared to the ATRIA Bleeding Risk Score, ORBIT Bleeding Risk Score, and HASBLED score.
- e. To evaluate adverse events such as major bleeding, stroke, death and cognitive disorders (Mild Cognitive Impairment or dementia), on the long term, namely: 3 years.

Hypothesis:

- a. We expect to find a rate of known AF of approximately 20%, and to find newly detected AF in 4 to 5% of the screened population.
- b. We expect to find a rate of paroxysmal AF of 45 to 60%.
- c. We expect that the baseline level of NTproBNP or BNP will be predictive of the development of new AF, especially when combined with the findings of the comprehensive geriatric assessment (CGA) and CHA₂DS₂Vasc score.
- d. We expect a rate of major bleeding of 3-5% per year.
- e. We expect that the ABC bleeding score, using age, GDF-15 and high sensitive Troponin T, will be predictive of major bleeding in the geriatric population.

Design:

- a. Prospective multicentre cohort study
- b. We aim to include 1250 geriatric ambulatory patients
- c. Inclusion period will last for 6 months, with a consecutive follow up period of 6 months, at 3 years patient files will be accessed for adverse events
- d. Scheduled commencement of the study is October 2020
- e. Blinding: none
- f. Randomization: none

Ethical board:

- a. The Commission Human Bound Research region Arnhem-Nijmegen, The Netherlands, has exempted the protocol as a 'niet WMO-plichtig onderzoek'.
- b. The record number of this decision is: 2019-5889.

Methods:

- a. The PPG measurements will be performed with a specially designed app, this research app will be developed by Happitech. Every participating center will receive a smartphone in order to install the application.

- b. All newly referred patients of 65 years and older that visit geriatric outpatient services are eligible (including Fall clinic, Memory clinic, Pre-operative geriatric assessment clinic, or any other geriatric outpatient clinics that are led by a geriatrician).
- c. Patients will be sent printed informative material about the project together with their appointment details. This material includes the informed consent form. They are asked to read the material, and fill out the informed consent form at home. At arrival to the outpatient clinic remaining questions will be answered, and the informed consent form collected, scanned, and added to their electronic medical file.
- d. Inclusion criteria:
 - a. The patient is able and willing to give written informed consent or allows a representative to do so in their name.
 - b. The paper copy will remain at the outpatient clinic to serve as a backup.
- e. Exclusion criteria:
 - a. The patient has a pacemaker or implantable cardioverter defibrillator.
 - b. The patient is known with a severe dementia, MoCA \leq 15 points.
 - c. The patient has a severe tremor, from whatever cause, and thus is unable to use the PPG based smartphone AF detection algorithm.
- f. Exclusion from analysis:
 - a. Less than three measurements with the PPG based smartphone AF detection are performed.
- g. Procedure (See also Figure 1, on page 5):
 - a. All participating patients will be allocated a study number. The allocation of study numbers will be coordinated by the research nurse, in collaboration with the local investigator and secretary. To ensure patient privacy, it is not allowed to use the hospital's patient number as the study number. Predefined study numbers will be provided to each centre.
 - b. The study number will be communicated with the physician by the secretary, and added to the electronic hospital files.
 - c. A CGA will be performed at baseline.
 - d. A 12 lead ECG will be performed at study entry to assess the baseline heart rhythm.
 - e. At every visit to the outpatient service one measurement with the PPG based smartphone AF detection algorithm will be performed.
 - f. The application will be made available for patients to install on their own smartphone, or their caretaker's.
 - g. Before each measurement the physician/patient/caretaker enters the patient's study number into the PPG app, which allows the investigators to register which measurement belongs to which participant, without accessing their medical files.
 - h. Coded, raw data will be analysed by the app, and results automatically sent by email to the principle investigator ([name]).
 - i. The smartphone shows the measurement in real time. In case of artefacts due to movement or otherwise, the PPG based smartphone AF detection algorithm will reveal this and a repeat measurement will be performed.
 - j. In case the PPG based smartphone AF detection algorithm detects AF, a 12 lead ECG is performed to confirm and document the diagnosis of AF and appropriate treatment will be initiated by the treating physician.

- k. If AF is detected at home, patients will be invited for the 12 lead ECG in the outpatient clinic.
 - l. Only patients who are known with AF and have an ECG or Holter registration showing AF in their medical record will be classified as patients with 'known AF'.
- m. Patients will be classified as 'newly detected AF' if AF is detected by the PPG device and consecutively confirmed on a 12 lead ECG. These ECGs will be periodically collected by the research nurse, in order to be reviewed to confirm the diagnosis for research purposes, by an independent cardiologist ([name] or [name]).
- n. All positive measurements with the PPG based smartphone AF detection algorithm, will be assessed by an independent cardiologist ([name] or [name]).
- o. Patients known with AF will also be screened with the device in the same fashion, making it possible to estimate the proportion of paroxysmal AF, but a confirmatory ECG will not be necessary as AF is already documented in those patients.
- p. In patients with newly detected AF, the algorithm will still be used in follow up visits, in order to determine the rate of paroxysmal AF.
- q. At study entry the baseline characteristics will be collected, including:
 - i. Medical history and medication use (as part of the CGA).
 - ii. MoCA.
 - iii. Functional measures such as pattern of gait and muscle weakness (as part of the CGA) and basic measurements such as weight and blood pressure (as part of the CGA)
 - iv. Standard blood samples including kidney function, blood count, electrolytes and INR if applicable. Blood will be taken during the routine blood sampling, to assess the HS Troponine T, NTproBNP and GDF-15 at an external location (Dijklander Hospital). A separate protocol can be found on page 6 of this protocol.
- r. Information about the study will be available in print at every participating centre. This information folder is added as an attachment.
- s. Of all patients at least 3 measurements with the PPG based smartphone AF detection algorithm will be collected, including the measurement at study entry, during a 6 months follow-up period. After 3 years adverse events will be assessed.
- t. A designated research nurse will have access to the code list (patient identifier and study code) at each participating centre collect participating centres, collect data on the baseline characteristics, and the measurements with the PPG based smartphone AF detection algorithm.

[figure not shown]
h. Frailty will be calculated as a Frailty Index, based on the accumulation of deficits model. It will incorporate a combination factors: functional, cognitive, physical and social. As proposed in literature (4. Searle et al., 5. Rockwood et al.), a number between 30 and 40 factors will be used to calculate the index. A detailed list of the variables and their definition is added as an attachment.

i. A detailed plan for the statistical analysis can be found on page 7 of this protocol.

j. Statistical analysis will be performed by [name], geriatrician at the Dijklander Hospital, and PhD student at the Free University in Amsterdam, under supervision of the principal investigators.

- k. First draft of the manuscript will be written by [name], geriatrician at the Dijklander Hospital, and PhD student at the Free University in Amsterdam, in collaboration with the principal investigators.
- l. Privacy: To protect patient privacy patients will be assigned a unique study code. The key to the code will be stored at a secure location at each hospital with limited access. Only coded data will be used for any data processing. The Board of Directors of the participating hospitals will be asked for approval the protocol. In addition, they will also be asked to appoint the research nurse for 0 fte (without salary) in their hospital.
- m. After 3 years, all patient files will be checked for the occurrence of: incident major bleeding, stroke, death or cognitive disorders (mild cognitive impairment or dementia + subtypes).

Figure 1. Study protocol

Laboratory Protocol

For the Dutch GERAF health care innovation project

As part of the Comprehensive Geriatric Assessment blood samples are taken. The number of measurements may differ between the participating centres, for example in which vitamins are analysed.

For the Dutch GERAF health care innovation project the standard laboratory testing should include measurement of:

Hemoglobin in mmol/L

eGFR in mL/min

TSH in mU/L

FT4 in pmol/L

Glucose in mmol/L

HbA1C in mmol/mol

INR

For study purposes one extra Lithium Heparine tube should be drawn, during the standard blood sampling.

This extra Heparine tube should be frozen at -20 degrees Celcius and stored after sampling at the participating centre.

The following extra analyses will be performed, for research purposes only:

GDF-15 in pg/mL

NT-proBNP in pg/mL

High sensitive Troponin T in ng/L

All samples will be transported to the Dijklander Hospital and will be analysed there by the Diagnostic Centre West Friesland (DCWF).

After analysis, [name] will collect the outcomes and add them to the anonymised dataset.

Costs for the analysis and storage will be covered by Roche Diagnostics.

Statistical analysis plan

1. Automated generation of variables, based on collected data:

1. CHA₂DS₂VASc score
2. HAS-BLED score
3. ORBIT Bleeding Risk Score
4. ABC Bleeding Score
5. ATRIA Bleeding Risk Score
6. Class of impaired renal function

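### Newly detected AF is not split into AF found at the entry visit and AF found only on repeat screening, so the planned pooled rate will not show what repetition adds

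*Combined protocol and SAP*

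**What the plan says.** The Background section gives the primary goal two parts: to estimate the rate of newly detected AF with the smartphone app, and "to determine if repeated screening for AF should become standard geriatric practise". Aim a is "To determine the rate of newly detected AF with repeated screening using a PPG based smartphone AF detection algorithm during follow-up visits".

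The Methods (g. Procedure) define the pieces:

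- Item d: "A 12 lead ECG will be performed at study entry to assess the baseline heart rhythm".
- Item e: one PPG reading at each outpatient visit, which includes the first.
- Item l: known AF requires an ECG or Holter recording of AF already in the medical record.
- Item m: newly detected AF is AF found by PPG and then confirmed on a 12-lead ECG. No reading number or time window is attached.
- Item s: at least three PPG readings per patient, "including the measurement at study entry, during a 6 months follow-up period".

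Hypothesis a states a single expected figure: "to find newly detected AF in 4 to 5% of the screened population". SAP 2.1 compares sinus rhythm with known AF at baseline. SAP 3.1 compares patients in sinus rhythm throughout with all newly detected AF as one group. SAP 3.2 and 4 add regression models. None of these sections separates the first reading from later ones.

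**The concern.** AF that is present on the day of the entry visit can be found by one reading, or by the entry ECG, at that visit. Only AF that was absent or missed at entry and found later can be credited to repeating the screen. The definition in items l, m and s lets both kinds count as newly detected, while the wording of aim a points to follow-up visits only.

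If one pooled 4 to 5% is reported and read as the yield of repeated screening, a recommendation on repetition could rest on cases that needed no repetition. Aim b does not cover this. Under items o and p it follows rhythm after AF is already known or detected. A patient found at entry who is later in sinus rhythm counts as paroxysmal, yet repetition did not find that patient.

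**Working it through.** **Plan's own figures.** The 4 to 5% and the target of 1250 patients are stated without a derivation, so there is no calculation to reproduce.

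**Inputs.** Target 1250 (Design, b). Known AF about 20% and newly detected AF 4 to 5% (Hypothesis, a). The share of new cases found at entry is not in the documents, so it is assumed over a range.

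**Step 1: base.** 1250 × (1 − 0.20) = 1000 patients without known AF. At 4% and 5% this gives 40 and 50 new cases, with Wilson 95% CIs of 3.0 to 5.4% and 3.8 to 6.5%.

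**Step 2: split.** For entry share f and x new cases, repeat-only cases are r = x(1 − f), rounded to whole patients. The denominator is those AF-free at entry, 1000 − (x − r).

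| Assumed entry share | Pooled 5%: repeat-only yield (95% CI) | Pooled 4%: repeat-only yield (95% CI) |
|---|---|---|
| 0% | 50/1000 = 5.0% (3.8 to 6.5) | 40/1000 = 4.0% (3.0 to 5.4) |
| 25% | 38/988 = 3.8% (2.8 to 5.2) | 30/990 = 3.0% (2.1 to 4.3) |
| 50% | 25/975 = 2.6% (1.7 to 3.8) | 20/980 = 2.0% (1.3 to 3.1) |
| 75% | 12/962 = 1.2% (0.7 to 2.2) | 10/970 = 1.0% (0.6 to 1.9) |
| 90% | 5/955 = 0.5% (0.2 to 1.2) | 4/964 = 0.4% (0.2 to 1.1) |

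The same pooled rate fits every row of its column, so it does not identify the repeat-only yield. Using all 1250 as the base changes little: at 5% (62 cases) and a 90% entry share, 6/1194 = 0.5%.

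**Step 3: can the range be narrowed?** Only with added assumptions. One scenario applies the 45 to 60% paroxysmal rate (Hypothesis, b) to new cases, puts all other AF at entry, and gives a paroxysmal patient an independent chance p of being in AF at each of three readings. The share of detected paroxysmal cases first found after reading 1 is 1 − p/(1 − (1 − p)³):

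- p = 0.1: 1 − 0.1/0.271 = 0.63
- p = 0.3: 1 − 0.3/0.657 = 0.54
- p = 0.5: 1 − 0.5/0.875 = 0.43

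Multiplied by 0.45 to 0.60, this is 0.19 to 0.38 of new cases. Multiplied by 4 to 5%, it is about 0.8 to 1.9% of patients.

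The scenario is fragile. Three readings is a minimum (item s), and home use is allowed (item f). With ten readings at p = 0.1 the share is 1 − 0.1/(1 − 0.9¹⁰) = 0.85. Then 0.85 × 0.60 = 0.51, and 0.51 × 5% = 2.5%, which is already outside that range.

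**The case against.** Three points on the other side carry weight.

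**The data permit the split.** A reader might infer that the study cannot show what repetition adds. The documents do not support that. There is an entry ECG (item d), an entry PPG reading (item s), and later readings tied to each study number (item g). A within-patient estimate is therefore possible; it is simply not planned.

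**Aim a may already exclude entry cases.** A reader might take it as settled that the primary rate counts AF found at entry. That follows from items l, m and s, but aim a's "during follow-up visits at a geriatric outpatient center" points the other way, and SAP 2.1 has no group for AF first found at entry. The passages conflict, and neither reading can be called the intended one. Figure 1 was not available in the text reviewed and should be checked. If entry cases are meant to be excluded, no rule says so.

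**Cumulative yield is a legitimate result.** The first half of the primary goal asks for the rate with the app, and a cumulative figure answers that. It does not answer the second half.

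Two further inferences go too far. Item d makes the ECG a study-entry procedure; nothing says it is usual care in these clinics, so a single ECG is not necessarily the comparator for a repeated-screening policy. Nor do the documents support saying that an entry ECG would find most cases, because they give no entry share. The 0.8 to 1.9% above should not be quoted as an estimate. It depends on exactly three independent readings, no onset during follow-up, and a paroxysmal rate whose denominator is not stated. It also ignores the need for ECG confirmation, which an intermittent case may miss.

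**Conclusion.** The concern holds as a gap in the endpoint definition and the SAP. Items m and s do not separate AF found at entry from AF found only on repeat screening, this conflicts with aim a, and no planned analysis makes the split. The pooled rate will therefore not show what repetition adds, although that is half of the primary goal.

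The size cannot be fixed from the documents. With 1000 patients without known AF and a pooled 5%, the repeat-only yield runs from 5.0% to about 0.5% as the assumed entry share goes from 0 to 90%; at a pooled 4% it runs from 4.0% to 0.4%. These figures assume full recruitment, no loss through the three-reading rule, and the plan's 20% known AF. The change should be made: it bears on the study's main conclusion and needs little beyond wording.

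**What to change.** 1. Reconcile aim a with items m and s, and state whether AF found at entry counts towards the primary rate.
2. Beside the cumulative rate, report (1) new AF found at entry, on the entry ECG and/or a confirmed entry PPG reading, and (2) AF first found at reading 2 or later among patients without known AF who were AF-free on both the entry ECG and the entry PPG. Give each its own denominator and 95% CI.
3. Add a table of cumulative confirmed new AF by reading number, with the number of patients contributing at each reading, since the count will vary between patients.
4. Base the statement on the added value of repetition on (2).
5. Amend item m to classify AF seen on the entry ECG with a negative PPG reading. As written it is neither known nor newly detected.
6. State that the exclusion of patients with fewer than three readings (Methods, f) does not remove entry-detected cases from (1).

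**Cost.** Protocol and SAP wording and one table. No new patient procedure is needed, but the order of readings must be kept with each result. Entry ECGs showing AF without a positive PPG would have to join the independent review in item m. The figure credited to repetition will be smaller whenever any case is found at entry, and its interval relatively wider: at a 50% entry share, 2.6% (1.7 to 3.8) against a pooled 5.0% (3.8 to 6.5).

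### Nothing keeps the person who judges major bleeding at 3 years from seeing the research biomarkers and risk scores that the bleeding outcome is meant to evaluate

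*Combined protocol and SAP*

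**What the plan says.** - **Design, item e:** "Blinding: none". No scope is given (allocation, outcome assessor or analyst). The next item says that there is no randomisation.
- **Aim d** is worded as follows: "To evaluate the predictive value of the ABC Bleeding Risk Score, compared to the ATRIA Bleeding Risk Score, ORBIT Bleeding Risk Score, and HASBLED score". SAP 2.2 does this by area under the ROC curve and by sensitivity, specificity and predictive values at preset cut-offs. SAP 4.3 adds models for death, major bleeding and their composite.
- **Hypothesis e:** the investigators expect ABC, built from age, GDF-15 and hs-troponin T, to predict major bleeding in these patients.
- **Methods, item m (3-year follow-up):** "After 3 years, all patient files will be checked for the occurrence of: incident major bleeding, stroke, death or cognitive disorders". The text does not say who checks, how major bleeding is defined, whether there is a second reader, or what the checker may see.
- **Laboratory Protocol:** the extra tube is dealt with as follows: "This extra Heparine tube should be frozen at -20 degrees Celcius and stored after sampling at the participating centre". The assays are introduced with "The following extra analyses will be performed, for research purposes only". Once they are done, a named member of the study team "will collect the outcomes and add them to the anonymised dataset". No date is given for the assays or the merge.
- **SAP 1:** the risk scores are generated automatically from the collected data, again without a date.
- **Methods, items g.m and g.n:** an independent cardiologist reviews confirmatory ECGs and positive PPG measurements. No such review is planned for bleeding.

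**The concern.** Deciding from a hospital file whether a bleed was major takes judgement, and the protocol text offers no definition to narrow it. If the person deciding knows the patient's ABC score, or the biomarkers behind it, doubtful cases may be called in line with that score. The outcome would then partly reflect the predictor, and the comparison in aim d and SAP 2.2 would no longer be a fair test. The bleeding models in SAP 4.3 would be affected in the same way. Death needs little judgement, and the primary goal (newly detected AF) is not affected.

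This exposure is avoidable. GDF-15, hs-troponin T and NT-proBNP are research assays whose results go to a coded dataset, so the file checker does not need to see them.

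**Working it through.** The plan states no figure to reproduce. The check has two parts: whether access before the file check is realistic, and how large an effect could be.

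**1. Order and access**

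- Inclusion lasts 6 months and AF follow-up a further 6 months (Design, item c), so AF data are complete 6 + 6 = 12 months after the start. Files are checked at 3 years (36 months). Counted from study start, the gap is 36 − 12 = 24 months. Counted per patient, it is 36 − 6 = 30 months.
- Aim c uses NT-proBNP, and SAP 4.2 uses NT-proBNP and/or GDF-15, to predict newly detected AF. That analysis can run about two years before the file check and needs those values in the dataset. GDF-15 is an ABC component.
- hs-troponin T is not needed for the AF analysis. It is measured from the same extra tube, so it may well arrive at the same time, but the text does not say so.
- Methods g.b puts the study number in the electronic hospital file. A file reader who also has the coded dataset can therefore find the patient's row. No text separates those two roles.

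**2. Size**

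*Events.* With N = 1250 and 3 to 5% per year (hypothesis d), 1250 × 3 × 0.03 = 112.5 and 1250 × 3 × 0.05 = 187.5. That is about 110 to 190 bleeds if all patients are used, before deaths and exclusions from analysis.

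*Assumptions, none from the documents.* Every score has a true AUC of 0.65. A share f of recorded bleeds is borderline and unrelated to ABC. Unmasked, these are called only when ABC is above its median. ABC and a comparator are normal scores with correlation ρ of 0.3 to 0.5.

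- Masked, either score: AUC = (1 − f) × 0.65 + f × 0.50. At f = 0.10 this is 0.635.
- Unmasked, ABC: AUC = (1 − f) × 0.65 + f × 0.75. At f = 0.10 this is 0.660. The change from masked calling is 0.25f.
- Unmasked, comparator: among the borderline events its AUC is 0.5 + asin(ρ/√2)/π, which is 0.568 at ρ = 0.3 and 0.615 at ρ = 0.5.
- Gain of ABC over the comparator: f × (0.75 − 0.568) or f × (0.75 − 0.615).

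| f | ABC against masked calling | ABC against comparator, ρ = 0.3 | ρ = 0.5 |
|---|---|---|---|
| 0.05 | 0.0125 | 0.009 | 0.007 |
| 0.10 | 0.025 | 0.018 | 0.014 |
| 0.15 | 0.0375 | 0.027 | 0.020 |

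Calling only above the median is the extreme case. If three quarters of the borderline calls fall above the median, ABC's AUC among them is 0.75 × 0.75 + 0.25 × 0.25 = 0.625 instead of 0.75. The gains halve, to about 0.007 to 0.009 at f = 0.10.

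*A second model.* A simulation of 2,000,000 records assumed that 5, 10 or 20% of bleeds outside the top third of ABC are missed. The AUC of ABC was about 0.657, 0.663 and 0.677, against about 0.65 for a comparator. The shift is roughly 0.01 to 0.03. Here the comparator was independent of ABC given bleeding status, so it shared none of the rise, and these figures lean high.

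**The case against.** The strongest reply has four parts.

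1. **The order is not stated.** A reader might infer that biomarkers and scores are merged before the file check as a matter of plan. The documents do not say this. The tube is frozen, the merge follows laboratory analysis at an unstated time, and score generation is undated. All three could come after the check. This stands: early availability is an inference from the 6-month AF analysis, and a firmer one for NT-proBNP and GDF-15 than for hs-troponin T or a finished ABC score.
2. **Access is not shown.** Events come from the patient file, while the biomarkers go to a coded dataset. No text returns results to the file or gives the checker the dataset. This also stands, but no text prevents access either, and the study number in the file makes linkage easy.
3. **The blinding line may only mean that there is no allocation to blind.** That is a natural reading beside the line on randomisation, and it would be wrong to treat the item as a decision to unmask outcome review. The gap remains on either reading, because no other text masks the file check.
4. **Direction is open.** A reader might infer that ABC must be favoured. History, medication, kidney function and blood count are routine data, available to a file reader. Knowing them could favour the other scores, and the same arithmetic would then apply with the sign reversed. This stands. Those data cannot be hidden from a file reader, but the research biomarkers can.

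The 0.025 change at f = 0.10 should not be taken as the bias in the comparison. It is measured against masked calling at 0.635. Against the assumed true AUC of 0.65 it is 0.660 − 0.650 = 0.010, and correlated comparators would rise too.

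**Conclusion.** The point holds as an unprotected step in the plan. The outcome that decides the ABC comparison comes from a file check whose assessor is not kept from the research biomarkers or the scores, and those data are probably available in part by then. The documents do not show that any call will be influenced, and they settle neither direction nor size.

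Under the assumed inputs, the shift in ABC's AUC relative to a comparator is about 0.01 to 0.02 around f = 0.10, and 0.007 to 0.027 across the table. These figures assume extreme calling behaviour and halve under the milder case. A shift of that order could matter when scores of similar performance are compared. The matter concerns a secondary aim. It deserves a change because the remedy is cheap and masking cannot be restored once files have been read unmasked.

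**What to change.** Replace Design item e with:

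> No allocation to blind. Outcome assessment: whoever checks the files at 3 years has no access to the research biomarkers or any calculated risk score. The 3-year event data are kept in a separate file and linked to biomarkers and scores only after the events are locked.

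Methods item m should also name the role that does the check and the definition of major bleeding that applies.

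**Cost.** This is a protocol edit and an order of data access. Because the event file is held apart, rather than the biomarker file, the 6-month AF analysis is not delayed. The downside is that whoever handles the biomarker data cannot also judge events. That task would go to existing study staff without dataset access, such as the research nurse or local investigator. The documents do not show who has access now, so the sponsor needs to confirm that such a person is available at each centre. Routine clinical data in the file stay visible to the reader, so the change removes only the avoidable part of the risk.
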